## **11.0 Vulnerable Populations\***

N/A

## 12.0 Local Number of Subjects

A total of 70 subjects will be enrolled (35 in each study group). This sample size provides 80% power to detect a medium effect size in number of missed treatment fractions between study groups. Only subjects who meet eligibility criteria will be enrolled.

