## **4.0 Study Endpoints\***

### Primary Study Endpoints:

- Total number of missed fractions, determined via EMR
- A break in cancer treatment, defined as missing  $\geq 3$  fractions due to patient condition, determined via EMR
- ER visits, as determined via EMR
- Inpatient and outpatient hospital encounters, as determined via EMR
- Hospital readmission for the same presenting issue, as determined via EMR
- Hospital length of stay (if hospitalized), as determined via EMR
- Cancer treatment adherence, determined via EMR
- Medications for cancer treatment symptom management, determined via EMR
- Cancer treatment-related side effects, determined via EMR
- Patient-rated pain measured by visual analog scale, as determined via EMR
- Cancer treatment tolerance, measured by the Eastern Cooperative Oncology Group (ECOG) Performance Status score, as determined via EMR
- Quality of Life, as measured by the McGill Quality of Life Measure, administered in-person at weeks 1 and 12  
[\(http://www.npcrc.org/files/news/mcgill\\_quality\\_of\\_life.pdf\)](http://www.npcrc.org/files/news/mcgill_quality_of_life.pdf)

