## 14.0 Withdrawal of Subjects\*

Any study patient who experiences a safety endpoint under section 4.0, including recommendation to stop physical activity by treating oncologist, will be withdrawn from the study. Final, non-physical activity measures will be collected on patients who are withdrawn.

As Maple Tree provides free services to patients undergoing cancer treatment, a patient withdrawn from the study for safety reasons could, at a later date and when it is deemed safe by her physician, again receive exercise services at Maple Tree (outside the study context).

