### Data Analysis Plan:

Data will be analyzed using IBM SPSS Statistics version 25.0. Continuous variables will be described using mean, median, standard deviation, and range. Nominal variables will be described using frequency and percentage.

Baseline demographic and clinical characteristics will be compared between treatment and control groups to establish equivalence; any statistically significant differences between study groups will be controlled statistically. Continuous endpoints will be tested for normality using Shapiro-Wilk tests. Differences between study groups on continuous endpoints will be evaluated using independent samples *t*-tests for normally distributed endpoints and Mann-Whitney *U* tests for non-normally distributed endpoints. Nominal endpoints will be compared between groups using chi-square tests. Alpha will be set to .05, two-tailed for all tests.

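### The 80% power claimed for a 'medium' effect with 35 per group is not reproduced: at an assumed d = 0.5 the planned t-test has about 54% power

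*Combined protocol and SAP*

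**What the plan says.** Section 12.0 fixes the size of the trial: "A total of 70 subjects will be enrolled (35 in each study group"). The randomisation list in Appendix A also counts 35 and 35. The justification is a single sentence: "This sample size provides 80% power to detect a medium effect size in number of missed treatment fractions between study groups". No section defines medium, and Section 12.0 names no test, mean, SD, distribution or allowance for loss.

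The Data Analysis Plan in Section 17.0 supplies the remaining inputs. On the error rate: "Alpha will be set to .05, two-tailed for all tests". On the test: "Differences between study groups on continuous endpoints will be evaluated using independent samples" t-tests if the endpoint is normally distributed, and Mann-Whitney U "tests for non-normally distributed endpoints". The powered endpoint is the first primary endpoint in Section 4.0: "Total number of missed fractions, determined via EMR".

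On withdrawals, Section 14.0 says: "Final, non-physical activity measures will be collected on patients who are withdrawn".

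**The concern.** A two-group comparison with 35 per arm is well short of what is normally needed for 80% power at d = 0.5, the usual reading of a medium difference between two means. Either another meaning was intended and not written down, or the power is overstated.

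This is the only sample-size justification in the document. A reader of a null result would take it to mean that a medium benefit had an 80% chance of being detected. If the true chance is nearer one in two, a non-significant result says much less about whether exercise reduces missed fractions.

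**Working it through.** **Inputs.** n = 35 per group (Section 12.0); alpha .05 two-sided and an independent-samples t-test (Data Analysis Plan); stated power 80% (Section 12.0). *Assumed:* medium means d = 0.5, with a range shown. All 70 patients are taken to contribute.

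**1. Attempt to reproduce 80% at d = 0.5.** The noncentrality is d / √(2/n) = 0.5 / √(2/35) = 0.5 / 0.239 = 2.09.
- Normal approximation: power = Φ(2.09 − 1.96) = Φ(0.13) = 55.2%.
- Exact noncentral t on 68 df: 54.1%.

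The stated 80% is not reproduced. The chance of missing d = 0.5 is 100 − 54 = 46%.

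**2. Range of d (noncentral t, two-sided .05).**

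| d | Power with 35 per group | Patients per group for 80% |
|---|---|---|
| 0.4 | 37.8% | 100 |
| 0.5 | 54.1% | 64 |
| 0.6 | 69.7% | 45 |
| 0.68 | 80.1% | 35 |

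The normal-approximation check on the detectable difference is (1.96 + 0.84) × √(2/35) = 0.67; the exact value is 0.679.

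**3. Other conventional meanings of medium, 70 patients, two-sided.** ANOVA f = 0.25 gives 54.1%, arcsine h = 0.5 gives 55.2%, chi-square w = 0.3 gives 70.9%, and correlation r = 0.3 gives 71.7%. A regression f² = 0.15 with group as the only predictor gives 89.1%; this equals d = √(0.15 × 70 / 17.5) = 0.77. A one-sided t-test at d = 0.5 gives 66.5%.

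Readings that land near 80% are a paired t-test with dz = 0.5 (82.0% at 35 pairs), a one-sided correlation of 0.3 (81.3%), a two-predictor regression with f² = 0.15 (81.7%), and covariance adjustment with a covariate correlated 0.7 with the outcome (82.3% at d = 0.5). The plan specifies none of these for this endpoint.

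**4. Mann-Whitney.** On normal data its relative efficiency is 0.955, so 35 per group acts like 33.4. Power at d = 0.5 is about 52%, and 80% needs d = 0.679 / √0.955 ≈ 0.70.

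On counts, power depends on the shape. The shapes below are illustrative assumptions (35 per group, 20,000 simulated trials each).

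| Assumed distribution | d | t-test | Mann-Whitney |
|---|---|---|---|
| Normal | 0.50 | 53.7% | 51.9% |
| Negative binomial, means 2 v 1, dispersion 1 | 0.50 | 56.4% | 48.3% |
| Zero-inflated negative binomial, excess zeros 50% v 82.5%, mean 3, dispersion 3 | 0.50 | 56.7% | 74.5% |
| Zero-heavy (non-zero values 1–3, with 15% equal to 15), zeros 40% v 75% | 0.39 | 39.5% | 82.1% |
| Same shape, zeros 40% v 84% | 0.52 | 62.2% | 97.2% |

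For the negative binomial row, the variances are 2 + 2² = 6 and 1 + 1² = 2, so the pooled SD is √4 = 2 and d = (2 − 1)/2 = 0.5.

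**5. What a null result could exclude.** The half-width of the 95% interval for the mean difference is t(.975, 68 df) × √(2/35) = 0.477 SD. An estimate favouring exercise by more than 0.5 − 0.477 = 0.023 SD therefore has an interval that includes 0.5 SD. This too is a normal-theory figure.

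**6. Loss of patients.** At d = 0.5 the t-test has 49.7% power with 10% loss and 45.1% with 20% loss.

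**The case against.** The strongest reply is that this is under-specification, not a demonstrated miscalculation. The value d = 0.5 is not in the protocol; if the sponsor meant about 0.68, the 80% is right. That stands, and it limits the conclusion to a figure that cannot be reproduced. It does not rescue the sentence, because nothing in the document points to 0.68.

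A second reply is that the t-test is probably not the test that will be used. Missed fractions is likely to be skewed with many zeros, Shapiro-Wilk would then reject normality, and Mann-Whitney would apply. For some zero-heavy shapes it exceeds 80% at d near 0.4 or 0.5. This also stands, but for other plausible shapes it falls below the t-test figure. Without a stated distribution, neither outcome can be claimed.

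Two smaller points are fair. Section 14.0 describes follow-up of patients withdrawn for safety and does not clearly cover those who simply drop out, so full contribution is a condition of the figures above and not an established fact. And a confidence interval for the difference is not in the current analysis plan, so asking for one adds a small reporting step.

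**Conclusion.** The concern holds. The 80% in Section 12.0 does not follow from the design and tests the protocol states. Assuming d = 0.5, roughly normal data and all 70 patients contributing, power is about 54%, a shortfall of 26 percentage points. The trial has 80% power only for d = 0.68. The conclusion depends on the assumed meaning of medium and on the distribution of the counts, and the protocol gives neither. This should be corrected because no other sample-size argument exists and the statement will shape how a null result is read.

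**What to change.** Replace the power sentence in Section 12.0 with wording such as:

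> With 35 per group, an independent-samples t-test at two-sided .05 has 80% power for a standardised difference of 0.68 in missed fractions, and about 54% power for 0.5, assuming approximately normal data and that all patients contribute. The power of the Mann-Whitney test depends on the distribution of the counts.

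Then add:

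> A non-significant result will be interpreted through the 95% confidence interval for the between-group difference.

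If the 80% came from a particular count distribution or another value of medium, state that basis there instead: the effect measure and its value, the expected distribution in each group, the test, and the number expected to contribute.

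The cost is two sentences and a less favourable power figure. The restatement needs no extra patients and leaves the planned tests as they are. The interval is a small reporting addition, and if Mann-Whitney is used the protocol should say which difference it refers to and how it is computed. If the sponsor does want 80% power for d = 0.5 by the t-test, rewording will not provide it: that target needs 64 per group, 128 in total.

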## 13.0 Recruitment Methods

- 13.1 Eligible patients will be contacted in person when they are at KMC or Soin MC for regular appointments. If in-person appointments are not convenient times, patients may be contacted by phone by the research coordinator.
- 13.2 The research coordinator will attend breast tumor conferences to identify eligible patients and seek physician approval to approach the patients about study participation.
- 13.3 *A printed Interest Form will be provided to patients in their initial Breast Cancer Journey packets and during the Breast Cancer Class.*
- 13.4 The subjects will not receive compensation for their participation in the study.

## 14.0 Withdrawal of Subjects\*

Any study patient who experiences a safety endpoint under section 4.0, including recommendation to stop physical activity by treating oncologist, will be withdrawn from the study. Final, non-physical activity measures will be collected on patients who are withdrawn.

As Maple Tree provides free services to patients undergoing cancer treatment, a patient withdrawn from the study for safety reasons could, at a later date and when it is deemed safe by her physician, again receive exercise services at Maple Tree (outside the study context).

## 15.0 Risks to Subjects\*

The risks associated with the study intervention are commensurate with light to moderate physical activity, such as muscle soreness. Given the low-impact nature of the exercise and the one-on-one supervision during exercise sessions, the risk of injury or another adverse outcome is very low. Participants in the Exercise Group will have an exercise program individualized to their needs and physical abilities, and participants will be closely monitored during exercise sessions. The

**PROTOCOL TITLE:** Randomized, Controlled Trial of an Individualized Exercise Oncology Program for Newly Diagnosed Breast Cancer Patients

study will not be blinded; patients and treating physicians will be aware of group status and if the treating oncologist recommends the subject stop physical activity, the subject will be withdrawn from the study.

The Exercise Group may incur some travel costs to attend exercise sessions.

No psychological, social, or legal risks are anticipated.

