### Safety endpoints are:

- Objective worsening lymphedema due to physical activity, as determined by treating oncologist
- Pathologic fracture
- Recommendation to stop physical activity by treating oncologist

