## 5.0 Study Intervention/Investigational Agent

### Exercise Group

The study intervention is a supervised, individualized exercise oncology program described in previous literature and provided by Maple Tree Cancer Alliance, a non-profit organization providing exercise training to individuals with cancer (<https://www.mapletreecanceralliance.org/>). This organization was founded in 2011 and currently operates in 9 hospitals serving Ohio and Pennsylvania, offering free exercise programs and nutritional guidance to approximately 500 patients annually to help relieve side effects related to cancer treatment.

Patients in the supervised, individualized exercise oncology program (Exercise Group) will complete a 60-minute exercise session once per week for 12 weeks at Maple Tree Cancer Alliance. The exercise sessions will be individualized to the patient's needs and fitness level by a trainer with a bachelor's degree in exercise science and a national certification for exercise oncology. A patient will work with the same trainer throughout the study, who will plan the patient's individualized exercise regimen, and who will provide one-on-one supervision for the duration of each 60-minute session. Each 60-minute session will include cardiovascular, strength, and flexibility training.

Cardiovascular exercise will be performed on a treadmill. The intensity level for the aerobic exercise ranges from 30-45% of the individual's predicted VO2max, controlled by heart monitors (model S810i; Polar Electro) and lasting 30 min. Strength training will involve a full body workout, with emphasis on all major muscle groups and employing machines, free weights, and resistance tubing. Patients will complete 3 sets of 10 repetitions for each strength exercise. Flexibility training will involve static stretching of all major muscle groups for 15-20 seconds at the completion of each workout.

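### An exercise injury is counted as a harm only if it reaches one of three safety endpoints; lesser injuries, falls and in-session symptoms have no defined collection or attribution

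*Combined protocol and SAP*

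**What the plan says.** Section 15.0 describes the risk in general terms: "The risks associated with the study intervention are commensurate with light to moderate physical activity, such as muscle soreness". It then says that "the risk of injury or another adverse outcome is very low". It gives no rate and cites no source for one.

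Section 4.0 has three safety endpoints:

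- "Objective worsening lymphedema due to physical activity, as determined by treating oncologist"
- "Pathologic fracture"
- "Recommendation to stop physical activity by treating oncologist"

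Among the primary endpoints in Section 4.0, the one that concerns side effects reads "Cancer treatment-related side effects, determined via EMR". Other primary endpoints carry no restriction by cause. They include "ER visits, as determined via EMR", inpatient and outpatient hospital encounters, and a patient-rated pain scale.

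The secondary endpoints take two items from the exercise provider's participant records: session adherence and program attrition. Section 8.0 names quality of life and session adherence as the information gathered outside the medical record, and adds fitness assessments that are reported back to the Exercise Group. Section 5.0 assigns each patient a trainer "who will provide one-on-one supervision for the duration of each 60-minute session".

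Section 14.0 withdraws any patient who meets a Section 4.0 safety endpoint. Section 18.0 marks safety monitoring as not applicable. Section 17.0 describes no adverse-event form, grading, attribution or safety analysis.

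**The concern.** The exercise program is the treatment under test, yet the plan has no general means of recording what that treatment does wrong. A sprain, a fall from the treadmill, a strain from the weights or a symptom that cuts a session short is a plausible harm of this intervention. Unless the oncologist then advises stopping, none of these is a safety endpoint. They do not fit the side-effect endpoint either, because they do not come from cancer treatment.

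If the plan is followed exactly, the report could show no safety endpoints in the Exercise Group although injuries had occurred, and a reader could take that as support for the low risk stated in Section 15.0. A patient who drops out after an injury, without the oncologist's advice to stop and without seeking care, would be visible only as attrition. Section 3.0 places the trial in the context of making exercise oncology part of routine care. A hospital weighing that step would want an injury rate, and the trial could not supply one.

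**Working it through.** No figure in the plan is at stake, so the main check sets kinds of event against the Section 4.0 lists.

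| Event in the Exercise Group | Counted as a harm? | Could appear elsewhere? |
|---|---|---|
| Injury after which the oncologist advises stopping | Yes, third safety endpoint (no cause restriction) | Emergency visits, encounters, pain |
| Pathologic fracture, or worsening lymphedema due to activity | Yes, named | Same |
| Traumatic fracture or sprain with an emergency visit, no advice to stop | No | Emergency visits or encounters, without a link to exercise |
| Fall or symptom that ends a session, no care sought | No | Possibly pain scores |
| Muscle soreness | No | Possibly pain scores |
| Patient leaves the program after an injury, no advice to stop, no care sought | No | Attrition, without a reason |

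The last four rows are the gap. Pain, emergency visits and encounters are analysed as efficacy or utilization outcomes, and nothing in Section 17.0 ties an individual event to a session.

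**Exposure that goes unused.** Inputs: 35 patients in the Exercise Group (Section 12.0) and one session a week for 12 weeks (Section 5.0).

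- Full attendance: 35 × 12 = 420 one-on-one sessions.
- At the 70% adherence hypothesised in Section 2.0: 0.70 × 420 = 294 sessions.

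**What a log could state if no injury occurred.** For 0 events in n = 35 patients, the exact upper limit solves (1 − p)^35 = α:

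- Two-sided 95%: 1 − 0.025^(1/35) = 10.0%.
- One-sided 95%: 1 − 0.05^(1/35) = 8.2%.

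**Chance that there is something to record.** The plan gives no injury rate, so the per-patient 12-week risk p is an assumption, shown over a range. The chance of at least one injured patient among 35 is 1 − (1 − p)^35:

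| Assumed p | At least one injured patient |
|---|---|
| 1% | 29.7% |
| 2% | 50.7% |
| 5% | 83.4% |
| 10% | 97.5% |

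At an assumed risk of 2% or more, at least one injury is more likely than not. These figures assume that all 35 patients are observed and that injuries in different patients are independent.

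**The case against.** The strongest case against the point has four parts.

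- **Injuries are not wholly missed.** A reader might infer that no exercise injury would ever be counted as a harm, or that injury and soreness touch no endpoint at all. The documents do not support either reading. The advice-to-stop endpoint is not restricted by cause, so an injury that prompts such advice is counted. Pain, emergency visits and hospital encounters are also unrestricted and are compared between randomised groups. This stands. What is missing is any collection below that threshold, and any attribution.
- **Safety is not an objective.** Section 2.0 has no safety hypothesis, and Section 3.0 gives the prospective analysis of cost savings as the purpose. Section 15.0 mentions injury only to say that it is unlikely. This is fair, and the gap does not affect the efficacy comparison. But the plan does define safety endpoints, and their coverage is open to review.
- **The program is low intensity and supervised, and the protocol rates it as minimal risk.** How much minor-event logging such a trial needs is partly a matter of judgement. This argues for a light log. It does not argue for having none when a trainer is present throughout each session.
- **The yield is imprecise.** With 35 patients, zero events would still leave an upper limit of 8% to 10%, too wide to establish a very low risk. This stands too. A count with a wide interval is nevertheless more than the plan can report now.

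**Conclusion.** The point holds in a limited form. Exercise-related injuries count as harms only when they reach one of the three Section 4.0 safety endpoints, in practice an oncologist's advice to stop. Other injuries, falls and in-session symptoms have no defined collection or attribution, so the trial could not state an injury rate for its own program from as many as 420 supervised sessions.

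The consequence is an undercount of harms and a risk statement in Section 15.0 that the trial cannot test. No primary result changes. The conclusion rests on the text of the endpoint lists and the data plan. Trainers may note injuries informally, but the plan neither says so nor uses such notes. The size of the undercount cannot be given, because the documents contain no injury rate.

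**What to change.** - **Add a separately headed, descriptive recorded-harm item.** It would cover any injury, fall or symptom that ends or shortens an exercise session or leads to medical care, logged by the trainer in the participant records.
- **Keep it expressly outside the Section 4.0 safety-endpoint list.** Section 14.0 withdraws anyone who meets an endpoint on that list. Adding minor events there would change the withdrawal rule and inflate attrition, itself a secondary endpoint. A separate item leaves the rule as it is.
- **Ask both groups one question at week 12**, at the in-person quality-of-life contact already planned: any injury since enrolment that needed medical care.
- **Record harm as its own reason for attrition.**
- **Report events per patient and per session with a confidence interval.** Sessions within a patient are not independent, so the per-patient figure should lead. For example, 0 of 35 would be reported with the upper limit of 10.0% (two-sided) or 8.2% (one-sided).

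The cost is one field in the provider's records, one question at an existing contact, and some protocol wording. The field assumes that the records have an entry for each session, which measuring adherence to scheduled sessions implies but the plan does not state. The main drawback is that detection will be more intensive in the Exercise Group, so only the week-12 item should be compared between groups. With 35 patients the interval will be wide. Soreness that neither shortens a session nor leads to care would remain uncounted, which is a reasonable threshold.

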## **16.0 Potential Benefits to Subjects\***

Participants in the exercise intervention may experience reduced pain and relief from other effects of cancer treatment, thus reducing breaks in treatment and hospital or ER visits. Participants may also experience improved energy and mood and may establish a positive behavioral pattern of physical activity that will extend beyond the study.

